1 GENERAL INFORMATION

1.1 Introduction

Acne vulgaris is the most common skin disease in patients with skin of color and second most common in Caucasian population¹. The global prevalence is thought to be as high as 60-80% in individuals 12-25 years of age^{1,2}. However, it is not limited to only teenagers but also to adults, especially adult females³. The pathogenesis of acne is multifactorial. Genetics may also play a role. The treatment pathway should be directed to different pathogenic factors including, excessive sebum production, hyper keratinization, *P. acnes*, and inflammation^{4,5,6,7,8}.

Winlevi is the first topical anti androgen and sebum inhibitor approved for acne vulgaris. However, we do not have any clinical experience with Winlevi in combination treatment for acne. Acne vulgaris is a multifactorial disease and topical retinoids and Benzoyl peroxide and topical clindamycin products have been mainstay treatments for acne in our clinical practices.

Therefore ,it is reasonable to study Winlevi with Duac gel in combination to emulate real life practice.

References:

- 2. Plewig G, Kligman AM: Acne and rosacea, ed 3. Berlin Springer, 2000.
- 4. Williams C, Layton AM: Persistent acne in women: implications for the patient and for therapy. Am J Clin Dermatol 2006;7:218-290
- 8. Lomholt HB, Kilian M: Population genetic analysis of *Propionibacterium acnes* identifies a subpopulation and epidemic clones associated with acne. PloS One 2010;5:e12277
- 9. Winlevi packge insert

WIN2023 (v.06feb2023) Page 3 of 14

1.2 Study Population

Ten (10) subjects with moderate to severe facial acne vulgaris.

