3 STUDY DESIGN

This is a two-center, open-label pilot study. All study subjects will receive both Winlevi and Duac gel gel at baseline. The duration of the study is 16 weeks and consists of a Screening, Baseline Visit, and five (5) Follow-up Visits at Weeks 4, 8, 12 and 16. The treatment period is 12 weeks and 4 weeks of safety follow up totaling to 16 weeks.

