8 STATISTICS

8.1 Sample Size Justification

A total of 20 subjects will be entered into the study. This is a pilot study and a formal justification for the sample size is not provided. The data from this study will provide important data for determining any trends regarding the safety and efficacy of study medication.

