8.2 Analyses

Statistical analyses will be conducted on an intent-to-treat basis (i.e., all enrolled subjects will be included in the analyses). All statistical tests will be two-sided and interpreted at a 5% significance level. Descriptive statistics (i.e., mean, standard deviation, etc.) will be provided for all continuous variables and frequencies for all categorical variables collected in this study. These will be presented by treatment group. Summary tables will be used to present patient population characteristics at Baseline; data from the study questionnaires will be included. The incidence and severity of adverse and/or unexpected events will be tabulated and a complete listing of all reports of adverse and/or unexpected events will be presented.

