8.3 Interim Analyses

No interim analyses will be conducted.

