9.2 Ethics

The appropriate IRB must review the Study Protocol and the Informed Consent Form prior to initiating the study. Any significant modifications to the IRB-approved protocol or informed consent must be made in consultation with the IRB.

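### Planned enrolment is 10 subjects in Section 1.2 and 20 in Section 8.1, and nothing in the protocol reconciles the two

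*Combined protocol and SAP*

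**What the plan says.** Section 1.2 (Study Population) consists of one statement: "Ten (10) subjects with moderate to severe facial acne vulgaris". The number appears in words and in digits.

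Section 8.1 (Sample Size Justification) states: "A total of 20 subjects will be entered into the study". It continues: "This is a pilot study and a formal justification for the sample size is not provided".

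Four other sections bear on how these figures are read:

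- Section 3 (Study Design): "This is a two-center, open-label pilot study", and "All study subjects will receive both Winlevi and Duac gel gel at baseline". There is one regimen, so neither figure can be the size of one of several arms.
- Section 8.2 (Analyses): "all enrolled subjects will be included in the analyses".
- Section 8.3 (Interim Analyses): "No interim analyses will be conducted".
- Section 9.2 (Ethics): "Any significant modifications to the IRB-approved protocol or informed consent must be made in consultation with the IRB".

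**The concern.** The number of subjects to be enrolled is a basic design figure, and the protocol gives two values for it. A team working from Section 1.2 would close enrolment at half the number in Section 8.1. A team working from Section 8.1 would enrol twice the number in Section 1.2. Either course could be called a departure from the other section, although Section 9.1 requires investigators to follow the protocol. Section 4.1 admits subjects from 12 years of age, which is a further reason for the number exposed to be unambiguous.

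The statistical consequence is limited but real. The primary result is a single percentage: the share of subjects with an IGA of 0 or 1 at week 16. How finely that percentage can be resolved, and how likely the study is to show a less common adverse event, depend directly on whether 10 or 20 subjects are enrolled.

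**Working it through.** **1. Can either figure be reproduced?** No. Section 8.1 gives no power, effect size, expected rate, standard deviation or dropout allowance, and it says that no formal justification is offered. The two figures can only be compared with each other: 20 / 10 = 2, a difference of 10 subjects.

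**2. Does another section reconcile them?** Each reading that might do so was checked against the text.

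| Reading | Relevant text | Result |
|---|---|---|
| Ten per center | Section 3 gives two centers; 2 × 10 = 20 | The arithmetic fits, but Section 1.2 has no per-center wording and no section gives a per-center number |
| Ten evaluable or completing, 20 entered | Section 8.2 analyses everyone enrolled | No evaluable or completer target is defined |
| Replacement of withdrawn subjects | Section 4.3 allows replacement only before treatment starts; Section 5.2.4 gives new subjects new numbers | Neither sets a target that would turn 10 into 20 |
| Section 8.1 takes precedence | It is the sample-size section and speaks of a total | It is more explicit, but the protocol has no rule of precedence |

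The first reading is plausible but remains an inference. The others have no support in the text.

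**3. Effect on the primary percentage.** One subject moves the percentage by 100 / n: 100 / 10 = 10 points, or 100 / 20 = 5 points.

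The protocol gives no expected response rate, so rates of 20% to 50% are **assumed** here for illustration. The exact (Clopper-Pearson) 95% interval for x responders out of n runs from the 2.5% quantile of Beta(x, n − x + 1) to the 97.5% quantile of Beta(x + 1, n − x). Widths are taken from unrounded limits.

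| Assumed rate | n = 10 | Width (points) | n = 20 | Width (points) | Ratio of widths |
|---|---|---|---|---|---|
| 20% | 2/10: 2.5 to 55.6% | 53.1 | 4/20: 5.7 to 43.7% | 37.9 | 1.40 |
| 30% | 3/10: 6.7 to 65.2% | 58.6 | 6/20: 11.9 to 54.3% | 42.4 | 1.38 |
| 40% | 4/10: 12.2 to 73.8% | 61.6 | 8/20: 19.1 to 63.9% | 44.8 | 1.37 |
| 50% | 5/10: 18.7 to 81.3% | 62.6 | 10/20: 27.2 to 72.8% | 45.6 | 1.37 |

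The factor of two therefore applies to the number of subjects. The loss of precision is smaller, at about 1.4.

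**4. Effect on the safety objective.** The chance of seeing at least one subject with an event of true incidence p is 1 − (1 − p)^n. The incidences are again **assumed**.

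- p = 5%: 1 − 0.95^10 = 40.1%, against 1 − 0.95^20 = 64.2%.
- p = 10%: 1 − 0.90^10 = 65.1%, against 1 − 0.90^20 = 87.8%.

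If no event of a given kind is seen, the one-sided 95% upper bound on its incidence is 1 − 0.05^(1/n): 25.9% with 10 subjects and 13.9% with 20.

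**The case against.** The strongest reply is that this is a wording slip with little consequence. The study is an uncontrolled pilot with no power claim, success threshold or stopping boundary tied to n. The denominator is whoever is enrolled, so the analysis can be run with either number. Two centers with ten subjects each gives exactly 20, and only Section 8.1 uses the word total, so a dropped per-center qualifier is a natural explanation. A reader looking for the enrolment target would go to the sample-size section and find one number there. The protocol sets no precision target and plans no confidence interval, so the intervals above measure something it never promised, at rates it never stated. The title and consent pages were also not available for review, so the number given to the IRB or to subjects is not known.

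Much of this stands. No calculation in the protocol is wrong, the analysis rule is clear, and the intervals are illustrations rather than a shortfall against a stated goal. The statement that nothing reconciles the figures applies to the text available.

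What does not follow is that the conflict can be left. The per-center reading makes the reader supply words that Section 1.2 lacks, in a section that describes the study's population and not a site's. If that reading is right, Section 1.2 still needs the missing words.

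**Conclusion.** The concern holds. Two current sections give different enrolment numbers, 10 and 20, and the available text neither reconciles them nor shows which was intended. The conflict itself rests on no assumption, and neither does the change in the weight of one subject from 10 to 5 percentage points. The interval widths depend on assumed response rates of 20% to 50%, and the adverse-event probabilities on assumed incidences of 5% and 10%. On those assumptions the exact interval for the primary percentage is about 1.4 times as wide at the smaller number.

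This is an inconsistency between two stated figures, not a faulty calculation, and it does not affect how the data will be analysed. It must still be corrected, because it leaves the study without a single enrolment target and only the sponsor can say which number was meant.

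**What to change.** State the one intended total in both Section 1.2 and Section 8.1. If ten per center was meant, say so in Section 1.2, for instance as 10 subjects at each of two centers, 20 in total.

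As an option, Section 8.1 could add the width of the exact 95% interval that the chosen number gives at one or two plausible response rates, so that readers know what precision to expect. No formal sample-size calculation and no additional enrolment are requested.

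The cost is a one-line text change. If the correction alters the number the IRB approved, the consultation that Section 9.2 requires for significant modifications also applies.

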2 STUDY OBJECTIVES

The objectives of this study are to observe the efficacy and safety of combination treatment of Winlevi and Duac gel as a treatment modality for moderate to severe acne.

Primary objective: Percent of subjects who are clear or almost clear on IGA scale at week 16.

Secondary objectives: 1. Percent of total lesion reduction at week 12 compared to baseline

- 2. Percent of inflammatory lesion reduction at week 16 compared to baseline
- 3. Percent of non-inflammatory lesion reduction at week 16 compared to baseline.
- 4. Tolerability measures such as, erythema, scaling, dryness, oiliness, burning/stinging, and pruritus.

3 STUDY DESIGN

This is a two-center, open-label pilot study. All study subjects will receive both Winlevi and Duac gel gel at baseline. The duration of the study is 16 weeks and consists of a Screening, Baseline Visit, and five (5) Follow-up Visits at Weeks 4, 8, 12 and 16. The treatment period is 12 weeks and 4 weeks of safety follow up totaling to 16 weeks.

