5.1.1 Assessment Schedule

	Screening	Baseline	Follow-up Visits	
	Visit 0 -30 days	Visit 1 WK 0	Visit 2, 3, 4 Wk 4, 8, 12,	Visit 5 Wk 16
ICF/HIPAA	Х			
Subject Demographics/Medical Hx/Height	Х			
Weight	Х			Χ
Inclusion/Exclusion Criteria	Х	Х		
Vital Signs	Х	Х	Х	Х
Urine Pregnancy Test	X ¹	Х	X ¹	X1
Acne IGA Lesion Counts² Tolerability³	X	х	x	Х
Study Medication; Dispense Collect		D	C D	С
DLQI		Х	х	Х
Concomitant medication/Treatment	Х	Х	Х	Х
Adverse Events	Х	X	Х	Х

- 1 Female subjects of childbearing potential.
- Lesion Counts: papules, pustules, nodules, open/closed comedones
 Peeling, erythema, dryness, oiliness, burning, pruritus

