5.1.3 Visits 2, 3, 4 (Weeks 4, 8, 12 ± 3 days)

- Concomitant Medication/Treatment
- Urine Pregnancy Test (if applicable)
- Adverse Events
- Vital Signs
- Collect Study Medication
- DLQI
- Assessments
 - Acne IGA
 - Lesion Counts
 - Tolerability

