5.1.4 Visit 5 (Week 16; ± 5 days)

- Urine Pregnancy Test (if applicable)
- Concomitant Medication/Treatment
- Adverse Events
- Vital Signs
- Weight
- DLQI
- Assessments
 - Acne IGA
 - Lesion Counts
 - Tolerability

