6 STUDY ASSESSMENTS

6.1 Primary Endpoint

The primary endpoint of this study is the percent of patients who achieve clear or almost clear on IGA at week 16.

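### The primary IGA is read at week 16, but the protocol does not settle whether subjects are then on treatment or four weeks past their last dose

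*Combined protocol and SAP*

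**What the plan says.** **Duration of treatment.** Section 3 is the only place that states it: "The treatment period is 12 weeks and 4 weeks of safety follow up totaling to 16 weeks".

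**Primary reading.** Section 2 gives the primary objective as "Percent of subjects who are clear or almost clear on IGA scale at week 16". Section 6.1 agrees: "The primary endpoint of this study is the percent of patients who achieve clear or almost clear on IGA at week 16".

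**Lesion endpoints.** Section 6.2 puts total, inflammatory and non-inflammatory lesion reduction at week 16. Section 2 puts inflammatory and non-inflammatory reduction at week 16 but total reduction at week 12.

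**Drug supply in the schedule.** In Section 5.1.1 the row "Study Medication; Dispense Collect" carries D at baseline, C and D in the single column headed "Visit 2, 3, 4 Wk 4, 8, 12", and C at week 16.

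**Drug supply in the visit lists.** Section 5.1.3, which covers weeks 4, 8 and 12, has "Collect Study Medication" and no dispensing. Section 5.1.4, for week 16, has neither collection nor dispensing.

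**Dosing text.** Sections 5.2.1 and 5.2.3 give how and how often to apply the products, but no stopping date.

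**The concern.** Section 2 says the study is meant to observe how well and how safely the combination works as a treatment. With no control arm, the primary result is one percentage, and its meaning rests on how long subjects were treated and when they were assessed. Response at the end of treatment and response four weeks after stopping are different quantities, and the protocol supports both readings.

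Under Section 3 the main efficacy assessment falls in a period set aside for safety follow-up. Supplement I bars topical retinoids, antibiotics, benzoyl peroxide and over-the-counter acne products throughout the study, so subjects could not use those in the gap. Any recurrence would lower the primary figure, which would then understate what the combination does while it is used.

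Week-16 tolerability changes meaning too: dryness, peeling or stinging four weeks after stopping is not tolerability in use. Finally, there are two centres. If they resolved the conflict differently, the pooled percentage would mix two estimands. The documents do not show that this will happen, but nothing in them prevents it.

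**Working it through.** No figure in the plan needs reproducing, beyond noting that Section 3's durations add up (12 + 4 = 16 weeks). The check compares the sections and then does the date arithmetic.

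**1. Sections side by side**

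| Source | Week 12 | Week 16 | Implied end of treatment |
|---|---|---|---|
| Section 3 | treatment ends | end of safety follow-up | week 12 |
| Section 5.1.1 | collect and dispense (shared column) | collect | week 16 |
| Sections 5.1.3 and 5.1.4 | collect, no dispensing | neither | leans to week 12 |
| Sections 5.2.1 and 5.2.3 | silent | silent | none stated |

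The visit lists cannot decide the matter. They show collection at weeks 4 and 8 with no dispensing, so read literally they would leave subjects without drug from week 4.

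**2. Time from last dose to the primary reading**

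Inputs: 12 weeks of treatment (Section 3); a window of ±3 days at week 12 (5.1.3) and ±5 days at week 16 (5.1.4).

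- Week 12 = 12 × 7 = day 84, window day 81 to 87.
- Week 16 = 16 × 7 = day 112, window day 107 to 117.
- Section 3 reading: nominal gap 112 − 84 = 28 days; shortest 107 − 87 = 20; longest 117 − 81 = 36. That is 4 of the 16 weeks (25%) off drug before the primary reading.
- Schedule reading: exposure of about 112 days (107 to 117), gap about 0.

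The two readings differ by four weeks, both in exposure and in time off drug.

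**3. Possible effect on the primary percentage**

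The documents give neither a relapse rate nor an expected response, so both are assumptions here. Write p for the response at week 12, r for the fraction of those responders lost by week 16, and g for the fraction of week-12 non-responders who become responders:

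week-16 response = p(1 − r) + (1 − p)g

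With g = 0:

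| p | r = 0% | r = 20% | r = 30% | r = 50% |
|---|---|---|---|---|
| 50% | 50% | 40% | 35% | 25% |
| 40% | 40% | 32% | 28% | 20% |

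For example, 50% × (1 − 0.30) = 35%. Late responders (g above 0) would offset some or all of the loss; at p = 50% the two cancel when g = r.

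**The case against.** The strongest reply is that Section 3 is the only explicit statement on duration and is perfectly clear, while the contrary reading comes from one row of a table. Weeks 4, 8 and 12 share a column, so the dispensing mark may not have been meant for week 12. On the end of treatment, the visit lists side with Section 3. This has some force, and week 12 may well be what was intended. But a separate collection mark at week 16 makes sense only if subjects still hold drug after week 12. And if Section 3 governs, the primary efficacy reading is certainly off treatment, so this argument removes the ambiguity but not the mismatch with the objective.

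Second, a post-course reading is a legitimate measure of a 12-week course. It is also not strictly persistence, because it counts anyone who first responds after week 12. Both points are fair. Such an endpoint would be acceptable if it were declared, but the protocol nowhere says so and calls those weeks safety follow-up.

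Third, this is a small descriptive pilot. With 20 subjects (Section 8.1; Section 1.2 says 10), a fall from 50% to 40% is two people. Exact 95% intervals are 27% to 73% for 10/20 and 19% to 64% for 8/20. Small losses would be hard to see, but a systematic shift in what is measured is not sampling noise, and wide intervals do not correct it.

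Fourth, Section 8.2 promises frequencies for every categorical variable, so the week-12 IGA should be tabulated anyway. That limits the harm. It does not make the week-12 result the primary one, nor tell the reader which visit ended treatment.

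**Conclusion.** The concern holds. As written, the protocol does not establish whether the primary IGA is an on-treatment or a post-treatment reading. On Section 3's explicit wording it is taken after treatment has stopped, nominally 28 days and between 20 and 36 days after the last dose. That does not match the stated aim of observing the combination as a treatment.

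The timing conflict rests on the documents alone. The effect on the percentage does not: the illustrated drop from 50% to between 50% and 25% depends on assumed relapse, an assumed week-12 response and no late responders. The true effect could be nil. Divergence between the centres is a possibility only. The week-12 versus week-16 disagreement over total lesion reduction is a further sign that the end of treatment was never fixed. This needs correcting before the study starts, because the primary result cannot be interpreted without it.

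**What to change.** 1. Choose one end of treatment and state it in Sections 3, 5.1.1, 5.1.3 and 5.1.4. Add the last day of application to Section 5.2.3. Give weeks 4, 8 and 12 separate columns in the schedule, so that dispensing and collection are clear for each.
2. Define the primary endpoint as IGA 0 or 1 at the visit that ends treatment, in both Section 2 and Section 6.1.
3. Time all three lesion-reduction endpoints to that visit, and remove the disagreement between Sections 2 and 6.2 on total lesions.
4. If a later visit remains, report its IGA, lesion counts and tolerability as named post-treatment secondary results.

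The simplest route keeps 12 weeks of treatment and moves the primary reading to week 12. It costs wording only, since IGA and lesion counts are already taken at weeks 12 and 16, and it keeps the four-week safety follow-up.

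Treating to week 16 instead is possible but costs more. At about 1 g of Winlevi twice daily (Section 5.2.3), four more weeks need 2 × 28 = 56 g per subject, roughly one further 60 g tube, plus additional Duac. It also removes the off-drug follow-up unless a visit is added. A significant modification by either route needs IRB consultation under Section 9.2 if the protocol is already approved.

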4 SELECTION AND WITHDRAWAL OF SUBJECTS

4.1 Inclusion Criteria

i. Outpatient, male or female subjects of any race, and at least 12 years of age or older. Female subjects of childbearing potential must have a negative urine pregnancy test result at Baseline (test must have a sensitivity of at least 25mIU/ml for human chorionic gonadotropin) and practice a reliable method of contraception throughout the study:

A female is considered of childbearing potential unless she is:

- postmenopausal for at least 12 months prior to study drug administration;
- without a uterus and/or both ovaries; or
- has been surgically sterile for at least 6 months prior to study drug administration.

Reliable methods of contraception are:

- hormonal methods or intrauterine device in use ≥ 90 days prior to study drug administration;
- barrier methods plus spermicide in use at least 14 days prior to study drug administration; or
- vasectomized partner (vasectomy must be performed 3 months prior to first study drug administration or in the alternative a zero sperm count will suffice)

[Exception: Female subjects of childbearing potential who are not sexually active will not be required to practice a reliable method of contraception. These subjects may be enrolled at the Investigator's discretion if they are counseled to remain sexually inactive during the study and understand the possible risks in getting pregnant during the study.]

- ii. Facial acne IGA score of 3 or 4.
- iii. Able to understand the requirements of the study and sign Informed Consent/HIPAA Authorization forms. Subjects under the legal age of consent in the state where the study is conducted must also have the written, informed consent of a parent or legal guardian.

WIN2023 (v.06feb2023) Page 4 of 14

4.2 Exclusion Criteria

- i. Female subjects who are pregnant (positive urine pregnancy test), breast-feeding, or who are of childbearing potential and not practicing a reliable method of birth control.
- ii. Allergy or sensitivity to any component of the test medications (Section 5.2).
- iii. Subjects who have not complied with the proper wash-out periods for prohibited medications (Supplement I).
- iv. Medical condition that, in the opinion of the Investigator, contraindicates the subject's participation in the clinical study.
- v. Skin disease/disorder that might interfere with the diagnosis or evaluation of acne vulgaris
- vi. Evidence of recent alcohol or drug abuse.
- vii. History of poor cooperation, non-compliance with medical treatment, or unreliability.
- Exposure to an investigational drug study within 30 days of the Baseline Visit.
- ix. Patients who have demonstrated hypersensitivity (e.g., anaphylaxis) to clindamycin, benzoyl peroxide, any components of the formulation, or lincomycin. (4) Patients with a history of regional enteritis, ulcerative colitis, or antibiotic-associated colitis (including pseudomembranous colitis)

